#### Neurological status

Neurological status will be evaluated both prior to the surgery and throughout the study.

Neurological status is based on four types of measurements (sections): motor, sensory, reflexes, and straight leg raising. Each of the sections is comprised of a number of elements. Following scales will be used to evaluate neurological status: reflexes (0 = Absent or Trace, 1 = Hyper-reflexic, 2 = Normal), sensory function (Light Touch or Pin Prick L1 to S1), motor function (using 0-5 scores 0-5 whereas 0= Total Paralysis, 1 = Palpable or Visible Contraction, 2 = Active Movement, Gravity Eliminated, 3 = Active Movement, Against Gravity, 4 = Active Movement, Against Some Resistance and 5 = Active Movement, Against Full Resistance (full strength) and straight leg raise (positive = patient experiences radiating leg pain below the knee on elevating the leg between 15 and 70 with the knee extended, normal = no pain is experienced on elevating the leg between 15 and 70 with the knee extended).

Overall neurological success will be defined as maintenance or improvement in all sections (motor, sensory, reflex, and straight leg raising) for the time period evaluated. In order for a section to be considered a success, each element in the section must remain the same or improve from the time of the baseline evaluation to the time period evaluated. Therefore, if any one element in any section does not stay the same or improve, then a patient will not be considered a success for neurological status.

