#### **G.1.2 Analysis of Secondary Endpoints**

For the first secondary objective, the similar method as the one outlined above for the primary endpoint will be used to assess whether the ODI improvement at 3 months is equivalent for the non-spondylolisthesis DDD subjects treated with anterolateral approaches and the ones treated with posterior approaches.

For secondary points ODI improvement at other follow-ups other than at 3-months visit; change of VAS back and leg pain intensity and EQ-5D at all follow-ups through 5-year visit, summary statistics will be provided and the paired t-test will be used to test whether the improvement at each follow-up from baseline is significant.

The neurological success rate will be summarized at each follow-up. Overall neurological success will be defined as maintenance or improvement in all sections (motor, sensory, reflex, and straight leg raising) for the time period evaluated. In order for a section to be considered a success, each element in the section must remain the same or improve from the time of the baseline evaluation to the time period evaluated. Therefore, if any one element in any section does not stay the same or improve, then a patient will not be considered a success for neurological status.

Time-to-event-analysis will be conducted for fusion success. The fusion success rate will be summarized for 1, 2, 3, 4, 5-year follow-up, if applicable. If a subject shows fusion success at early timepoints and non-fusion at a later timepoint, the fusion status at all earlier time points should be considered as non-fusion.

For 2-level subjects, fusion success will be defined as achieving fusion at both treated levels.

For secondary surgery at index levels, secondary surgery at adjacent levels and AEs, survival analysis will be performed to estimate the cumulative event rate up to 5 years.

Healthcare utilization will be measured with the following three cost components:

- (1) resources: procedure, length of hospital stay, additional medical visits (outpatient consultations, visits to primary care services, etc)
- (2) medications and
- (3) non-pharmacologic therapies: rehabilitation program

For time needed for first ambulation and surgery recovery day, summary statistics for continuous variable will be provided by subgroups.

The analyses for the primary endpoint and secondary endpoints outlined in secondary objectives 2 and 3 will be done for all subjects and the following subgroups:

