6.1.3. Analysis Datasets

The primary analysis dataset defined in this study comprises of all subjects who are enrolled and receive a single or double level instrumented fusion using MAST™ minimally invasive PLIF, TLIF, DLIF, OLIF, ALIF and MIDLIF surgical procedures with a mandatory posterior fixation. For double levels instrumented fusion, the same procedure must be used for both levels. All the analyses will be carried out on the

This document is electronically controlled. Printed copies are considered uncontrolled.

Confidential

primary analysis dataset. For subjects who are enrolled but not included in the primary analysis dataset, their demographic and other baseline characteristics will be summarized separately. The reasons for not using minimally invasive procedure or surgery not done will be listed as well.

In addition to the primary analysis dataset, four subgroups are defined in the following:

- 1) DDD patients with spondylolisthesis and stenosis
- 2) DDD patients with spondylolisthesis but without stenosis
- 3) DDD patients with stenosis but without spondylolisthesis
- 4) All patients not included in subgroups 1), 2), 3).

The analysis for the primary endpoint and secondary endpoints outlined in secondary objectives 2 and 3 (section 4.2) will be performed on these four subgroups as well. For the primary analysis dataset and each of these four subgroups, the analysis will be carried out on further subgrouped by anterolateral and posterior groups.

Other subgroup analysis such as by number of treated levels may also be performed.

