6.4. Handling of Missing Data and Dropouts

All data analyses will be based on the observed data. Missing data due to lost to follow-ups will not be imputed. For study subjects included in the primary analysis dataset who drop out or withdraw from the study, data collected before the occurrence of dropout or withdrawal will be included in analysis.

This document is electronically controlled. Printed copies are considered uncontrolled.

Confidential

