6.9.2.2.2. Neurological success

Neurological status is based on four sections: motor, sensory, reflexes, and straight leg raising. Each of the sections is comprised of a number of elements.

6.9.2.2.2.1 Motor Function

For the motor function, the assessments are listed in ascending order of improving as indicated below:

0 = Total Paralysis

1 = Palpable or Visible Contraction

2 = Active Movement, Gravity Eliminated

This document is electronically controlled. Printed copies are considered uncontrolled.

Confidential

3 = Active Movement, Against Gravity

4 = Active Movement, Against Some Resistance

5 = Active Movement, Against Full Resistance (full strength) (Normal)

For the time period evaluated, for each of elements, if the score increases from baseline, the subject is considered "improved"; if the score remains the same as baseline, the subject is considered "maintained"; if the score decreases from the baseline, the subject is considered "deteriorated". In the situation where the score at baseline is 0 (Total Paralysis) and a postoperative visit is missing, or the score at baseline is missing and at a postoperative visit is 5 (Normal), the subject is conservatively considered as "maintained". For overall motor status, if at least one element has the status of "improved" and the rest are "maintained", then the overall motor status is considered "improved"; if all elements have the status of "maintained", then the overall motor status is "maintained"; if at least one element has the status of "deteriorated", then the overall motor status is "deteriorated."

6.9.2.2.2.2 Sensory function (Light Touch or Pin Prick L1 to S1)

For the sensory function, the assessments include absent, impaired and present (normal) which are listed in ascending order of improving. Let absent be 0, impaired be 1 and normal be 2. The same logic outlined in the motor function section will be used to first determine the change status of each element from the baseline and then the overall sensory status from the baseline. For each element, in the situation where the score at baseline is 0 (Absent) and a postoperative visit is missing, or the score at baseline is missing and at a postoperative visit is 2 (Normal), the subject is conservatively considered as "maintained".

6.9.2.2.2.3 Reflexes

For the reflexes, the assessments are listed as indicated below:

0 = Absent or Trace

1 = Hyper-reflexic

2 = Normal

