For each element, a change from 0 (Absent or Trace) to 2 (Normal) or 1 (Hyper-reflexic) to 2 (Normal) is considered improved while the other way around is considered deteriorated. No change is considered maintained. Any change from 0 (Absent or Trace) to 1 (Hyper-reflexic) is considered "diminished to hyperactive" while the other way around is considered "hyperactive to diminished". In the situation where the score at baseline is missing and at a postoperative visit is 2 (Normal), the subject is conservatively considered as "maintained". If none of element has the situation of "diminished to hyperactive" or "hyperactive to diminished", an overall evaluation of reflex will be summarized using the same logic outlined in the motor function section. Otherwise, there will be no overall evaluation.

6.9.2.2.2.4 Straight leg raise

For the straight leg raise, the assessments include positive and negative (normal). Let positive be 0 and negative be 1. The same logic outlined in the motor function section will be used to first determine the

This document is electronically controlled. Printed copies are considered uncontrolled.

Confidential

change status of each element from the baseline and then the overall straight leg raise status from the baseline. For each element, in the situation where the score at baseline is 0 (Positive) and a postoperative visit is missing, or the score at baseline is missing and at a postoperative visit is 1 (Negative), the subject is conservatively considered as "maintained".

Overall neurological success will be defined as maintenance or improvement in all sections (motor, sensory, reflex, and straight leg raising) for the time period evaluated. In order for a section to be considered a success, each element in the section must remain the same or improved from the time of the baseline evaluation to the time period evaluated. If at least one section is deteriorated, the overall neurological success will be defined as failure.

Summary statistics (frequencies) will be presented for status of each section and overall neurological success at each follow-up.

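### A switch between absent and hyper-reflexic in one reflex leaves the whole reflex section unevaluated, so a recorded deterioration in another reflex is lost from the section table and from the stated failure trigger

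*SAP*

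**What the plan says.** Neurological success is one of the clinical outcomes under the second secondary objective (Protocol B.1.3; SAP 4.2). It is built from four sections: motor, sensory, reflexes and straight leg raise.

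- **Reflex elements (SAP 6.9.2.2.2.3).** Each reflex is scored 0 (absent or trace), 1 (hyper-reflexic) or 2 (normal). Moving to 2 is improvement, moving away from 2 is deterioration, and no change is maintenance. A move between 0 and 1, in either direction, has its own label and is none of these three. I call it a crossing.
- **Reflex section.** If no reflex shows a crossing, the section follows the motor logic of SAP 6.9.2.2.2.1, where a single deteriorated element makes the section deteriorated. If any reflex shows one: "Otherwise, there will be no overall evaluation".
- **Overall result (end of SAP 6.9.2.2.2.4).** For a section to be a success, "each element in the section must remain the same or improved from the time of the baseline evaluation to the time period evaluated". Failure is stated at section level: "If at least one section is deteriorated, the overall neurological success will be defined as failure".
- **Protocol.** The neurological status text in B.1.3 sets the same element condition, "each element in the section must remain the same or improve from the time of the baseline evaluation to the time period evaluated". G.1.2 adds that "if any one element in any section does not stay the same or improve, then a patient will not be considered a success". Neither mentions crossings.
- **Reporting.** Section status and overall success are tabulated at each follow-up. SAP 6.1.3 adds that "the analysis will be carried out on further subgrouped by anterolateral and posterior groups". On missing data, SAP 6.4 says "All data analyses will be based on the observed data".

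**The concern.** The crossing rule deals with a change that has no natural direction, since absent and hyper-reflexic are both abnormal. As written, though, it withdraws the status of the whole section and not only of the reflex that crossed. A different reflex may have gone from normal to abnormal at the same visit. That change has a clear direction, and without the crossing it would make the section deteriorated. With the crossing, it disappears from the section table and cannot reach the failure sentence through the reflex section.

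Two outputs are at stake. The reflex-section frequencies can omit deteriorations that were examined and recorded. The overall result has a group of patients whose class and place in the denominator are unstated. Both outputs are shown by surgical approach, and SAP 6.9.3 item 8 names neurological status as a possible outcome for regression on approach.

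**Working it through.** The plan gives no figure for this rule, so there is none to reproduce. The check applies the SAP rules literally, with motor, sensory and straight leg raise held at maintained.

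**Step 1. Classify one reflex.** Three baseline scores by three follow-up scores give 9 changes (baseline-follow-up):

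- maintained: 0-0, 1-1, 2-2 (3)
- improved: 0-2, 1-2 (2)
- deteriorated: 2-0, 2-1 (2)
- crossing: 0-1, 1-0 (2)

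Total 3 + 2 + 2 + 2 = 9.

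**Step 2. Worked case.**

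| Reflex A | Reflex B | Reflex section | SAP failure sentence met? | Element condition for success met? |
|---|---|---|---|---|
| 2-0 | unchanged | deteriorated | yes | no |
| 2-0 | 0-1 | unevaluated | no | no |
| unchanged | 0-1 | unevaluated | no | no |

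Rows 1 and 2 contain the same deterioration in reflex A. Only the added crossing in B changes the section result.

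**Step 3. All pairings.** Two deteriorating changes by two crossings give 2 × 2 = 4 mixed pairings. The section is unevaluated in 4 of 4. If a deteriorated element took precedence, it would be deteriorated in 4 of 4.

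**Step 4. More reflexes.** The documents do not state how many reflexes are tested, so the number k is an assumption. Of 9 changes per reflex, 7 are not deteriorations, 7 are not crossings, and 5 are neither.

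- Patterns with a deterioration: 9^k − 7^k
- Of these, patterns without a crossing, where the section is still deteriorated: 7^k − 5^k
- Lost: the difference

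| k | With a deterioration | Still deteriorated | Lost |
|---|---|---|---|
| 1 | 9 − 7 = 2 | 7 − 5 = 2 | 0 |
| 2 | 81 − 49 = 32 | 49 − 25 = 24 | 8 |
| 4 | 6561 − 2401 = 4160 | 2401 − 625 = 1776 | 2384 |

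These are counts of logical patterns, not patient frequencies. They show that the problem exists from two reflexes up.

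**Step 5. Effect on the success rate.** Let N be the patients examined, S the successes and V the patients with an unevaluated reflex section. No patient in V is a success, because a crossing is neither maintained nor improved. The rate is S/N if they are kept and S/(N − V) if they are dropped. The second is higher whenever V and S are above zero. The documents do not give V, and SAP 6.4 does not say whether an examined but unevaluated section counts as observed.

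**The case against.** **The patient is not counted as a success.** A reader might infer that the SAP contradicts the protocol and lets a deteriorated patient through as a success. The documents do not support that. The element condition in SAP 6.9.2.2.2.4 matches Protocol B.1.3 and G.1.2, and all three bar the patient in row 2 from success. The protocol asks for a success rate and defines no separate failure count. This stands in full.

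**Failure may still be assigned.** The SAP sentence gives one condition that is enough for failure and does not say it is the only one. A programmer who codes every non-success as a failure would keep the patient as a failure. So the stronger statement, that a second abnormal finding definitely removes a patient from the failure count, holds only if failure is coded from that sentence alone. What remains is that the SAP does not say which coding applies. The reflex-section table loses the deterioration under either coding.

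**Leaving a crossing unranked is deliberate.** The motor scale is ordered. Absent and hyper-reflexic are two kinds of abnormality that the SAP chooses not to rank, and the exception to the motor logic is explicit. That is defensible for a section with a crossing and no deterioration. It does not justify discarding a deterioration elsewhere, because under the motor logic one deteriorated element settles the section whatever the crossing means.

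**The case may be rare.** It needs a crossing and a deterioration in one patient at one visit. To affect the overall result, it also needs no deterioration in the other three sections. Protocol E.7 requires hospital visits only at 3 months and 1 year and allows telephone contact at the other follow-ups, when a reflex examination is unlikely. This is a fair limit on exposure, but the documents give no frequency either way.

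**Conclusion.** The point holds for the mixed case. Followed as written, SAP 6.9.2.2.2.3 drops a recorded reflex deterioration from the section frequencies and from the section-based failure trigger whenever another reflex crosses. This is the effect of a stated rule, so it is more than a missing detail. The unstated parts are whether such a patient is a failure and whether the patient stays in the denominator.

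The size in patients cannot be derived: neither the number of reflexes tested nor the frequency of crossings is given. It would be tempting to read the pattern counts as an effect size, or to conclude that the success rate is biased upward. Neither follows. The rate is unchanged if these patients are kept and rises only if they are dropped.

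The consequence is limited. The endpoint is descriptive with no hypothesis test (Protocol B.4; SAP 6.2), the regression on approach is optional, a deterioration in another section still triggers failure, and the primary ODI conclusion is untouched. The correction should still be made before analysis, because it is nearly free and the outcome is shown by surgical approach.

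**What to change.** Amend SAP 6.9.2.2.2.3 and the overall-success paragraph of 6.9.2.2.2.4 as follows:

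- **(a)** Any deteriorated reflex makes the reflex section deteriorated, whatever the other reflexes do, and so makes the patient a failure.
- **(b)** Keep the unevaluated status only for a section with a crossing and no deteriorated reflex. Count those patients as not a success, in line with Protocol B.1.3 and G.1.2, unless the SAP justifies treating a crossing as the same or better.
- **(c)** Keep all examined patients in the denominator at each visit, and report the number with an unevaluated reflex section by anterolateral and posterior group.

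The cost is a small change to the derivation and a few sentences of SAP text, with no new data. The reported failure count may rise; by how much cannot be said from the documents.

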## **G DATA ANALYSIS AND REPORTING**

### **G.1 Analysis of clinical data**

For the purpose of the analysis, all subjects who are enrolled and undergo a minimally invasive lumbar fusion procedure will be included in the analyses. All the analyses will be based on observed data. No missing data will be imputed.

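### For motor, sensory and straight leg raise, the SAP can score an unexamined patient as maintained, which conflicts with its no-imputation rule and slightly biases the section frequencies

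*SAP*

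**What the plan says.** **The element rules (SAP 6.9.2.2.2).** Each element is compared with baseline and called *improved*, *maintained* or *deteriorated*. Three sections also have a rule for a missing follow-up, which sets the element to *maintained*:

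- Motor: when "the score at baseline is 0 (Total Paralysis) and a postoperative visit is missing".
- Sensory: "in the situation where the score at baseline is 0 (Absent) and a postoperative visit is missing".
- Straight leg raise: "in the situation where the score at baseline is 0 (Positive) and a postoperative visit is missing".

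Reflexes have no such rule. Their only missing-data provision concerns a missing baseline: "In the situation where the score at baseline is missing and at a postoperative visit is 2 (Normal), the subject is conservatively considered as" *maintained*.

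**From element to section.** A section is *maintained* "if all elements have the status of" *maintained*. The motor section sets this logic, and sensory and straight leg raise reuse it. The SAP does not say what status a section has when some elements have none. Overall neurological success requires maintenance or improvement in all four sections, reflexes included. Frequencies are reported for each section and overall at each follow-up.

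**General missing-data statements.** Protocol G.1: "No missing data will be imputed". SAP 6.4 bases all analyses on observed data and adds: "Missing data due to lost to follow-ups will not be imputed". SAP 6.12 (changes to planned analysis) is marked not applicable, although Protocol G.1.3 asks for departures from the statistical plan to be documented with a justification.

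**The concern.** Giving a status to a patient who was not examined is imputation, so the neurological rule and the general statements cannot both be followed as written. The rule is also selective. It admits unseen patients on the strength of their baseline score, and the status it gives always falls on the success side. Unseen patients with a better baseline, who could have deteriorated, are left out. A patient who recovered but missed the examination is recorded as unchanged.

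At stake are the section frequencies for motor, sensory and straight leg raise at each visit. Success would be somewhat overstated and improvement understated, and more so where examinations are often missing. Protocol E.7 requires a hospital visit at 3 months and 1 year but allows a phone call at 4 weeks and at 2 to 5 years. The assessment schedule lists neurological status at every follow-up, and these are hands-on examinations.

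**Working it through.** The documents give no neurological rate and no missing-examination rate, so there is no planned figure to reproduce. The check has two parts.

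**1. Who enters a section rate.** Apply the SAP logic to a patient not seen at a visit, for straight leg raise with two elements (assumed to be left and right; 0 = positive, 1 = negative):

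| Baseline | Element statuses | Section status |
|---|---|---|
| 0, 0 | maintained, maintained | maintained |
| 0, 1 or 1, 0 | maintained, none | not defined |
| 1, 1 | none, none | not defined |

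Only the patient at 0 on every element receives a section status, and it can only be *maintained*. For motor this would need total paralysis on every element, and for sensory absent sensation on every element. I take both to be unusual, though the documents give no figure. Straight leg raise is the realistic case. The same patient has no reflex status, so overall success is not filled in.

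**2. Size, for a one-element section.** All inputs are assumptions, and missingness is taken as unrelated to baseline and outcome:

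- f = share at the worst score at baseline, 20%
- m = share not examined, 30%, 60% or 80%
- d = share deteriorating among the rest, 10%
- g = share improving among those at the worst score, 60%

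Formulas:

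- Success, observed only: S = 1 − d(1 − f)
- Success, with the rule: [(1 − m)S + mf] / [(1 − m) + mf]
- Improved, observed only: gf
- Improved, with the rule: (1 − m)gf / [(1 − m) + mf]

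At m = 30%: S = 1 − 0.1 × 0.8 = 0.920, and the denominator is 0.70 + 0.30 × 0.20 = 0.76. Success with the rule is (0.70 × 0.920 + 0.06) / 0.76 = 0.704 / 0.76 = 0.926. Improved is 0.6 × 0.2 = 0.120 observed, against 0.70 × 0.120 / 0.76 = 0.084 / 0.76 = 0.111 with the rule.

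| Not examined | Success: observed → rule | Improved: observed → rule |
|---|---|---|
| 30% | 92.0% → 92.6% (+0.6) | 12.0% → 11.1% (−0.9) |
| 60% | 92.0% → 93.8% (+1.8) | 12.0% → 9.2% (−2.8) |
| 80% | 92.0% → 95.6% (+3.6) | 12.0% → 6.7% (−5.3) |

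With f from 5% to 30% and m from 30% to 80%, the shifts run from +0.2 to +3.8 points for success and from −0.1 to −9.8 for improved. With less missingness (m 10% to 40%, f 10% to 50%, d 5% to 10%), they run from +0.05 to +1.25 and from −0.07 to −7.5. In a two-element section, f is the share at 0 on both elements, so it is smaller than the share positive on either leg.

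**The case against.** **A specific rule normally prevails over a general one.** That tells the programmer what to do, but it does not remove the conflict. Protocol G.1 makes no exception, SAP 6.4 does not mention one, and SAP 6.12 records no change.

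**An element at 0 cannot fall, so *maintained* is its worst possible result.** This stands. The SAP's description of the rule as conservative is right for the single element and for improvement. It fails only for the section success rate, because patients who cannot fail are added to the denominator while unseen patients who could have deteriorated are not.

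**The reach is narrow.** This also stands. A reader might infer that the rule covers any neurological element, or that one element at 0 brings an unseen patient into the rate. The text supports neither: reflexes have no missing-visit rule, and one element at 0 leaves the section undefined. A programmer who ignored missing elements would widen the effect, but the SAP does not instruct that.

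**The larger shifts need extreme inputs.** They do. The top of the range takes 80% unexamined and 30% at the worst score. Phone follow-up makes high missingness plausible at some visits, but no document gives a rate.

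**The clause might mean only an unscored element in a patient who was examined.** The SAP does not say whether the whole visit or one score is missing. This is a reason to clarify the wording.

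**Conclusion.** The point holds in a limited form. The clause exists in three of the four sections and conflicts with SAP 6.4 and Protocol G.1; that needs no assumed figure. Its effect on the section frequencies has a definite direction when missingness is unrelated to outcome: success up, improved down. The size is about +0.6 and −0.9 points at 20% at the worst score and 30% unexamined, and larger if many later examinations are missing. The sizes depend entirely on assumed rates and on a one-element section, and in practice they concern mainly straight leg raise.

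Two stronger conclusions are not supported. Overall neurological success is not inflated, because a wholly unseen patient has no reflex status. Nor do the documents show that the rule creates a difference between anterolateral and posterior groups. That would require missed examinations or baseline severity to differ between them, on which there is no information, and these summaries are descriptive. The primary conclusion, which rests on ODI at 3 months, is not affected.

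**What to change.** - In SAP 6.9.2.2.2.1, 6.9.2.2.2.2 and 6.9.2.2.2.4, delete the clause for baseline 0 with a missing postoperative visit for patients not examined at that visit.
- Report each section's frequencies with the number examined at the visit as denominator, and show that number.
- State how a section is scored when an examined patient has some elements missing. One option: *deteriorated* if any observed element deteriorated, otherwise section status missing. Without this, deleting the clause would leave partly examined sections undefined.
- If the present rule is wanted, keep it only as a labelled sensitivity analysis and name it as an exception in SAP 6.4.

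The cost is SAP wording only, with no new data. Denominators become smaller and section success rates slightly less favourable.
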